5.2. Analysis methods

Primary outcome 1: CRP at four weeks

We will analyze the change in CRP using a linear regression model, with change in CRP as the outcome, and three covariates: randomized treatment (binary), site (binary) and baseline CRP (linear). No other covariate adjustment will be made.

Primary outcome 2: Urgency syndrome at one-year

We will analyze the change in Urgency syndrome using a linear regression model, with change in Urgency syndrome score as the outcome, and three covariates: randomized treatment (binary), site (binary) and baseline Urgency syndrome score (linear). No other covariate adjustment will be made.

Secondary outcomes

All other analyses of secondary outcomes will be analyzed using the same method as for the primary endpoints.

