1.2. Objectives

1.2.1. Primary Objectives

There are two co-primary objectives:

Primary Objective 1: Investigate if the addition of 6 g psyllium husk, compared to placebo, will reduce the level of C-reactive protein (CRP) measured four weeks after the end of radiotherapy.

Primary objective 2: Investigate if the addition of 6 g psyllium husk, compared to placebo, will reduce the level of Urgency Syndrome measured one year after the end of radiotherapy.

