Power calculation: For both primary outcomes, we have recalculated the power based on an assumed dropout rate of 10% at 4 weeks after radiotherapy and 15% dropout rate at the one-year follow-up. Hence the power is based on sample sizes of 318 for CRP at 4 weeks and 300 for Urgency Syndrome at 12 months. We have used an alpha of 0.05 for both comparisons. For CRP at 4 weeks, following the results reported in Pal et al [14] we assume that in the control group CRP will increase by 400ng/mL, and that in the intervention group it will decrease by 700ng/mL, with a common SD of 3100. With these assumptions, we will have 88% to detect a difference. For Urgency Syndrome at 12 months, based on results we published in 2019 [15] we assume that at baseline the mean syndrome score will be -2.1 (SD=2.8) in both arms, but will increase during the study to 1.1 (SD=4.6) among the control group. Assuming that the intervention mitigates half of this increase, we estimate that in the intervention group, the mean urgency syndrome score will increase to -0.5 (SD=4.6). Hence the change in the two groups will be 3.2 and 1.6, respectively, with a common SD of 3.6. Under these assumptions, we will have 97% power to detect a difference.

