3.3. Analysis population

1. Intention-to-treat. This will consist of all randomized participants who initiated at least one task in the study, who will be analyzed according to their original assignment.
2. Per-protocol. Participants who consumed at least 80 percent of the capsules.

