5. ANALYSIS

5.1. Outcome definitions

5.1.1. Co-Primary outcomes

The co-primary outcome of change in concentration of hypersensitive CRP will be calculated as

$$\text{CRP at four weeks after the end of radiotherapy} - \text{CRP at baseline}$$

Hence, a positive value for the change will indicate an increase in CRP and a negative value will indicate a decrease.

The co-primary outcome of change in urgency syndrome will be calculated as

Urgency Syndrome at one-year after the end of radiotherapy – Urgency Syndrome at baseline

Higher scores of the Urgency Syndrome indicate worse symptoms. Hence a negative value for the change in Urgency score will indicate a worsening of symptoms over the duration of the trial, and a positive value will indicate an improvement in symptoms.

The Urgency Syndrome Score for each participant at each timepoint will be calculated using the factor loadings identified in Steineck et al [5].

All questions related to the urgency factor loadings in the paper by Steineck et al [5] are included in Fidura except one: 'Immediate need to defecate'. The reason is because it was very similar to the variable 'Sudden defecation urgency requiring lavatory'. The new question is on the same scale (1-7) as the old question, and we took the decision to substitute it without further amendments.

The urgency syndrome score for each participant and occasion is based on 14 questions, each of which is scored on a 1-7 scale, where 1 indicates the lowest level of symptoms and 7 the highest.

To calculate the score, first, for each participant and occasion, the variable will be standardized using the formula $X - \mu / \sigma$, where:

- X is the score for that participant for that specific question
- μ is the mean of that specific question from all participants (both arms) at the specific timepoint (baseline or follow-up)
- σ is the standard deviation of all responses (both arms) to that question at that timepoint

Then, each question will be multiplied by a loading factor. Finally, the scores will be summed up to a final score.

| Q # | Question text (translated from Swedish) | Loading factor |
|-----|---|----------------|
| 46 | Loose stools the last 3 months at baseline /the last week, 4 weeks after radiotherapy /the last three months, one-year after radiotherapy | 0.71 |

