5.4. Missing data

Missing data will not be imputed for the main analysis of primary and secondary outcomes. If there is an imbalance of missingness between the two randomized arms (defined as >20% difference between the missingness of an outcome between the arms), or if the overall missingness of an outcome variable is greater than 40% then we may perform multiple imputation as an exploratory analysis.

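### A participant with an observed follow-up value but no baseline value is dropped from every outcome model; a prespecified rule for missing baselines would keep them, at small gain and small cost.

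*SAP*

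**What the plan says.** Section 1.2.1 words the first co-primary objective as whether psyllium "will reduce the level of C-reactive protein (CRP) measured four weeks after the end of radiotherapy"; the second is likewise about a level, at one year. Section 5.1.1 then defines both outcomes as follow-up minus baseline, and section 5.1.2 carries this over to the secondary syndrome scores. In section 5.2 the CRP model reads "We will analyze the change in CRP using a linear regression model, with change in CRP as the outcome", with arm, site and baseline CRP as covariates. The Urgency model has the same form, and the secondary outcomes follow it.

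On missing data, section 5.4 states: "Missing data will not be imputed for the main analysis of primary and secondary outcomes". Multiple imputation is optional, exploratory and triggered only by missingness of an outcome.

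The intention-to-treat population in section 3.3 is "all randomized participants who initiated at least one task in the study, who will be analyzed according to their original assignment". It does not require a baseline value. The power statement in section 2.3 allows for "an assumed dropout rate of 10% at 4 weeks after radiotherapy and 15% dropout rate at the one-year follow-up", that is, for loss at follow-up. The SAP has no rule for a missing baseline and no figure for how many participants lack one.

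**The concern.** Section 3.3 admits a participant whom sections 5.2 and 5.4 then exclude. Someone who gave the four-week blood sample or answered the one-year questionnaire, but has no usable baseline, has the quantity named in the objective and still contributes nothing to the arm comparison. For the syndrome scores, that person's follow-up answers would even help set the mean and standard deviation used to standardize each question at follow-up (section 5.1.1) before the person is excluded.

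The cost is some precision and a departure from analysing everyone with an observed outcome as assigned. Recruitment stopped at 354 of a planned 500 (section 2.3), so avoidable losses deserve a look.

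**Working it through.** **1. The plan's own power.** Inputs from section 2.3: CRP difference 400 − (−700) = 1100, SD 3100, N = 318 (354 × 0.90 = 318.6); Urgency difference 3.2 − 1.6 = 1.6, SD of change 3.6, N = 300 (354 × 0.85 = 300.9); alpha 0.05, taken as two-sided. With equal arms, SE = SD × √(4/N) and power ≈ Φ(difference/SE − 1.96).

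- CRP: SE = 347.7, ratio 3.164, power 88.6% (88.4% with the 190:164 split). The SAP says 88%.
- Urgency: SE = 0.4157, ratio 3.849, power 97.1% (97.0% with the split). The SAP says 97%.

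Both figures reproduce.

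**2. Change or follow-up value.** Write the planned model as y − b = α + τ·arm + γ·site + β·b + e. Adding b to both sides gives y = α + τ·arm + γ·site + (β + 1)·b + e. Only the baseline coefficient moves, by 1. On one simulated data set with the SAP's Urgency values, both forms gave an arm estimate of −1.1438, SE 0.4426 and P = 0.0102; the baseline coefficient was −0.023 in one and 0.977 in the other.

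**3. Who is dropped.** Without imputation both forms need b. Over 3000 simulated trials of 300, both kept the same participants: on average 285 at 5% missing baseline and 270 at 10%. Changing the outcome alone recovers nobody.

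**4. What a filled baseline recovers (Urgency).** The implied correlation is r = (2.8² + 4.6² − 3.6²)/(2 × 2.8 × 4.6) = 16.04/25.76 = 0.62. The residual variance is σₑ² = 4.6²(1 − r²), so σₑ = 3.60; at an assumed r = 0.3 it is 4.39. Let m be the share of those followed up who lack a baseline, missing completely at random (the SAP gives no rate; 2% to 10% is assumed).

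- Dropping them: SE = √[4σₑ²/(N(1 − m))].
- Keeping them, with the pooled mean and an indicator: SE ≈ √[4((1 − m)σₑ² + m·4.6²)/N].

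| r | m | SE dropped | SE kept | SE cut | Power dropped → kept |
|---|---|---|---|---|---|
| 0.62 | 2% | 0.4198 | 0.4182 | 0.4% | 96.8% → 96.9% |
| 0.62 | 5% | 0.4264 | 0.4222 | 1.0% | 96.3% → 96.6% |
| 0.62 | 10% | 0.4381 | 0.4286 | 2.2% | 95.5% → 96.2% |
| 0.30 | 2% | 0.5118 | 0.5072 | 0.9% | 87.8% → 88.4% |
| 0.30 | 5% | 0.5199 | 0.5079 | 2.3% | 86.8% → 88.3% |
| 0.30 | 10% | 0.5341 | 0.5092 | 4.7% | 85.0% → 88.1% |

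Simulation of the fill-in with indicator agreed: SE cuts of 0.8% and 2.0% at r = 0.62 and of 2.3% and 4.3% at r = 0.3, for 5% and 10% missing. Mean estimates were about −1.59 against a true −1.6, with and without the dropped participants. A separate simulation at r = 0.62, with the mean fill-in but no indicator, gave power of 96.3% against 96.0% at 5% missing and 96.4% against 95.3% at 10%.

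**5. The non-parametric fallback.** Section 5.3 allows an equivalent non-parametric test if residuals look poor, and does not name it. The identity in step 2 belongs to least squares with baseline in the model; it does not carry over to an unadjusted rank test. As a normal approximation with 150 per arm:

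- On the change: 1.6/(3.6 × √(4/300)) = 3.849, power about 97%.
- On the follow-up value: 1.6/(4.6 × √(4/300)) = 3.012, power about 85%.

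**The case against.** The strongest reply is that the planned model is sound. It is unbiased and as precise as its follow-up-value twin, and nothing in the SAP shows that any participant lacks a baseline; section 2.7 simply says baseline data were collected. That stands, and it limits the point to a missing-covariate rule.

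Three stronger readings are tempting and not supported:

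- A reader might infer that defining the outcome as change is what loses participants. Step 3 shows otherwise: the baseline covariate and section 5.4 would lose the same people under either outcome. The change score matters only in that filling in a baseline would then also fill in part of the outcome, so the remedy needs the follow-up value as outcome.
- A reader might take the fall in power from complete data as the benefit at stake. For CRP, 5% or 10% missing baselines lower power from 88.6% to 86.9% or 85.1%. That compares dropping people with having full data; a filled baseline does not restore all of it. The gain for CRP cannot be computed, because the SAP gives no baseline SD or correlation for CRP.
- A reader might think that switching outcome has no downside at all. Step 5 shows that it would cost about 12 points of Urgency power if the fallback became an unadjusted rank test on the follow-up value.

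It is also fair to say that independence of baseline from assignment is assumed here. Section 2.7 times baseline relative to radiotherapy, but sections 2.1 and 2.2 do not say whether randomization or first capsule came after it.

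**Conclusion.** The point holds as a minor one. As written, sections 5.1, 5.2 and 5.4 together exclude from the co-primary and secondary models anyone in the section 3.3 population who has a follow-up value but no baseline. A fill-in rule for the covariate is a better method than exclusion. For Urgency it is worth roughly 0 to 1 power point at the correlation of 0.62 implied by the SAP, and about 0.5 to 3 points at an assumed 0.3. For CRP the size is unknown. If every baseline is present, the linear analysis does not change.

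This rests on an assumed 2% to 10% missing, on missingness unrelated to arm, on baseline being measured before it could be affected by assignment, and on the SAP's planning SDs. Even at an assumed 20% missing, dropping those participants leaves power at 80.8% for CRP and 93.1% for Urgency, so the trial's conclusions are not at risk.

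**What to change.** - **Sections 5.1 and 5.2:** for the linear models, take the value at four weeks (CRP) or one year (syndrome scores) as the outcome, with arm, site and baseline as covariates. This also matches the level wording of the objectives. Change from baseline can remain as a descriptive summary.
- **Section 5.4:** limit the no-imputation rule to outcomes. Replace a missing baseline value by the pooled both-arm baseline mean, add a missing-baseline indicator, and analyse everyone with an observed follow-up value.
- **Section 5.3:** state that the non-parametric fallback is baseline-adjusted or uses the change score.
- **Reporting:** give the number of filled baselines by arm, and confirm that baseline was collected before allocation could influence it.

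The cost is a few edited sentences in four sections and a few lines of code. The power statement in section 2.3 can stay in terms of change, because the arm effect in the linear model is the same quantity.

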5.3. Statistical principles

We will not adjust for any covariates other than the treatment indicator, site, the baseline value of the outcome, unless there is a large difference between the two groups at baseline. For binary variables, a “large difference” is defined as greater than a 20-percentage point absolute difference in the proportions. For a continuous variable, a “large difference” is defined as one randomization group having a value more than 20% higher than the other group. The randomized groups will be compared and confounding variables with $\geq 20\%$ difference between the groups will be included in the analysis.

We will visually assess the residuals for normality and homoscedasticity. If necessary, an equivalent non-parametric test will be performed.

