2.7. Timing of outcome assessment

Baseline data on CRP levels and urgency syndromes were collected two weeks prior to the start of radiotherapy, with outcome data gathered at multiple time points: immediately before, during, four weeks, and one year after treatment. The collection of data is presented in Figure 1. The primary CRP endpoint is measured at four weeks after radiotherapy. The primary urgency endpoint is measured one year after radiotherapy.

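### SAP 5.3 contradicts 5.2 on the covariates of both co-primary models, sets an imbalance rule that cannot be applied as written, and allows an unnamed non-parametric test of unstated role

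*SAP*

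**What the plan says.** SAP 5.2 specifies a linear regression of change for each co-primary outcome, with randomized treatment, site and the baseline value of that outcome as covariates. For each it adds: "No other covariate adjustment will be made".

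SAP 5.3 restates this limit but lifts it "unless there is a large difference between the two groups at baseline". A large difference is "greater than a 20-percentage point absolute difference in the proportions" for a binary variable, and "one randomization group having a value more than 20% higher than the other group" for a continuous one. The closing sentence of that paragraph says that confounding variables with a 20% or greater "difference between the groups will be included in the analysis". No such variables are listed.

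SAP 5.3 then has the residuals inspected by eye for normality and homoscedasticity, and continues: "If necessary, an equivalent non-parametric test will be performed". SAP 3.1 calls for 95% confidence intervals.

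Two other places bear on the rule. SAP 5.1.1 standardises each symptom question before summing, where the centring value "is the mean of that specific question from all participants (both arms) at the specific timepoint". SAP 2.7 says: "Baseline data on CRP levels and urgency syndromes were collected two weeks prior to the start of radiotherapy".

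**The concern.** Allocation was by simple randomization (SAP 2.2), so baseline differences between the arms are chance. A rule that adds covariates because of an observed difference lets chance choose the primary model. The size of an imbalance is also a poor guide to whether adjustment helps, since that depends on how strongly the variable predicts the outcome.

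The fallback raises a similar problem. After a poor residual plot, the SAP does not settle which p-value and which effect estimate are the primary ones. Two analysts could both follow the document and report different primary results for the same outcome.

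**Working it through.** **1. The plan's own figures.** SAP 2.3 gives no figure for this point, but its recalculated power reproduces (two-sided 0.05 assumed, equal arms).
- CRP: 1100 / [3100 × √(2/159)] = 3.16; 3.16 − 1.96 = 1.20, power 88.6% (stated 88%).
- Urgency: 1.6 / [3.6 × √(2/150)] = 3.85; 3.85 − 1.96 = 1.89, power 97.1% (stated 97%).

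Nothing below changes these.

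**2. The two sections side by side.** 5.2 excludes further covariates without qualification or cross-reference. 5.3 says imbalanced ones will be included. Both cannot govern the same model. The rule itself leaves open:
- which variables are candidates;
- whether the continuous comparison uses means or medians;
- what scale the closing 20% is on;
- what to do with variables of more than two classes, such as BMI, cytostatic treatment and smoking in the table of 4.4.

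**3. Binary rule, 190 v 164 (arm sizes from 2.3).** √(1/190 + 1/164) = 0.1066. At 50% prevalence the standard error is 0.5 × 0.1066 = 0.053, so 20 points is 3.75 standard errors. The exact binomial probability is 0.017%, and it is smaller at the lower prevalences checked (5 to 40%). If the closing 20% is read as relative, chance alone meets it in 9% of trials at 50% prevalence, 27% at 30% and 58% at 10%.

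**4. Continuous rule, 190 v 164.**
- Age (assumed mean 60 to 70, SD 8 to 12): from 0.20 × 60 / (12 × 0.1066) = 9.4 to 0.20 × 70 / (8 × 0.1066) = 16.4 standard errors. It would not fire.
- A log-normal variable such as baseline CRP (log-SD assumed; 40,000 simulated trials per setting):

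| log-SD | fires on means | fires on medians | readings disagree |
|---|---|---|---|
| 0.8 | 7% | 9% | 11% |
| 1.0 | 19% | 17% | 24% |
| 1.2 | 32% | 25% | 36% |

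**5. Syndrome scores.** Centring on the mean of both arms makes the pooled baseline mean zero over the full standardisation set: 190·m₁ + 164·m₂ = 0. The arm means then have opposite signs, and the gap relative to the size of the lower mean is 1 + 164/190 = 1.86 or 1 + 190/164 = 2.16. It exceeds 20% whatever the actual imbalance. On medians, simulation with the 14 loadings of 5.1.1 (assumed item-factor correlation 0.6) gives firing in 42 to 73% of trials. On means over a random 85% of participants it is about 97 to 98%.

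**6. Consequence if baseline CRP enters the urgency model.** The 300 of SAP 2.3 split in the ratio 190:164 is 161 v 139. With an assumed correlation of 0.1 to 0.3 with the outcome, the treatment estimate moves by a median 0.13 to 0.60 standard errors. The verdict changes in 2 to 8% of triggered trials with no effect. Over all trials that is roughly 0.02 × 0.07 = 0.1% to 0.08 × 0.32 = 2.6%.

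**7. Fallback, CRP.** The 318 split the same way is 171 v 147. The simulation assumed log-SD 0.8 to 1.2 and a baseline to follow-up correlation of 0.3 to 0.6. The 5.2 regression and an unadjusted Mann-Whitney test on change give different verdicts in about 5 to 8% of trials with no effect, and in 5 to 32% with an assumed 30% reduction. Each method taken alone has a type I error of 4.0 to 5.4%.

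**The case against.** The rule may be largely inert. Baseline CRP and the syndrome scores are not in the baseline table of 4.4. For the items that are, the explicit binary rule almost never fires and age does not trigger it. This stands, and it limits the size of the point. The 7 to 32% applies only if a skewed variable is a candidate, which 5.3 neither says nor excludes.

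A reader might infer that the rule always fires for syndrome scores. The SAP does not support that. It does not say that means are compared, and the set compared need not be the set used for standardising. Each outcome's own baseline score is also already in its model, so the matter arises only if another outcome's baseline score is a candidate.

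Mann-Whitney is only one reading of the fallback. 5.3 does not name it, and the SAP uses it only for the original sample-size simulation in 2.3. Because it drops site and baseline, part of the disagreement in step 7 reflects lost adjustment. That also stands. The figure illustrates what an unnamed test leaves open and does not predict what will happen.

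Finally, 5.3 can be read as an intended exception to 5.2. But 5.2 carries no such qualification, so the primary model still has two descriptions.

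**Conclusion.** Wrong as written, and it should be changed. Two parts need no assumption: 5.2 and 5.3 contradict each other on the covariates of both co-primary models, and the fallback has no name, criterion, effect estimate or stated role. The imbalance rule is also not operational, and a relative 20% threshold does not suit scores centred near zero.

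The size depends on what is a candidate. It is negligible for binary items under the explicit definition and for age. It is a chance trigger of about 7 to 32% for a log-normal variable with assumed log-SD 0.8 to 1.2, with mean and median readings disagreeing in 11 to 36%.

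Two stronger readings go too far. One is that the false-positive rate is inflated. Reporting the smaller of a t-test and a Mann-Whitney p-value on a skewed null outcome would give about 8% (171 v 147, assumed log-SD 1), but 5.3 ties the switch to residuals, not to p-values. The other is that CRP must be analysed on a log or rank scale. The SAP gives no distribution for CRP, and its own power assumption is an additive difference of 1100 ng/mL with SD 3100.

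**What to change.** - Delete the imbalance rule from 5.3, so that treatment, site and baseline value are the sole primary adjustment for both co-primary outcomes.
- Report any imbalance-adjusted model only as a sensitivity analysis, with its baseline covariates named in advance.
- State before unblinding that the 5.2 regression is the primary analysis whatever the residual plots show. Robust standard errors may be fixed now if wanted.
- Name any non-parametric analysis, make it covariate-adjusted, give its effect estimate, and label it a sensitivity analysis that does not replace the regression.

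A log or rank analysis of CRP is an optional choice for the sponsor, to be made before unblinding. It is not part of the required change. If it were chosen, the effect would no longer be a difference in mean change and 5.1.1 would have to match.

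The cost is SAP wording and a few sensitivity analyses, with no new data. Some power may be lost if CRP proves strongly skewed and the raw-change regression is kept. SAP 2.5 describes follow-up as still under way, so the document itself shows no obstacle to settling this before unblinding.
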